6.1.1 Adverse Events

Adverse events include:

- an exacerbation (i.e., increase in the frequency or intensity) of a pre-existing illness, episodic event or symptom (initially recorded at the screening/baseline visit), that is detected after trial intervention
- occurrence of a new illness, episodic event or symptom, that is detected after trial intervention

Adverse events do NOT include:

- Medical or surgical procedures: the condition that leads to the procedure is the adverse event
- Pre-existing disease or a condition present before treatment that does not worsen
- Hospitalisation where no untoward or unintended response has occurred

Reporting of Adverse Events

The patient population includes preterm infants who are cared for on a neonatal intensive care for a prolonged period. Due to the nature of the patient population, a high incidence of adverse events can be foreseeable during their hospital stay. Only adverse events deemed as serious (see section 6.1.2) or as notifiable event (see section 6.2) will be recorded for the trial.

6.1.2 Serious Adverse Events

6.1.2.1 Foreseeable (expected) SAEs

The following are 'Foreseeable SAEs' that could be reasonably anticipated to occur in this population of infants during the course of the trial or form part of the outcome data.

They do not require expedited reporting by trial centres as SAEs **unless considered causally related** to the intervention (NEL) in which case they should be reported within 24 hours of site staff becoming aware of them as detailed in section 6.3.2.

'Foreseeable SAEs' that are **casually related** to the trial intervention (NEL) should be reported within 24 hours of site staff becoming aware of them using the SAE report form.

Foreseeable SAEs that are **not considered causally related** to the trial intervention (NEL) should be reported within 5 working days. Therefore, all Foreseeable SAEs occurring for patients in Arm B (Temporising device alone) will be not related to NEL and should be reported within 5 days.

Foreseeable SAEs:

- Necrotising enterocolitis or gastrointestinal perforation
- Intracranial abnormality (intraventricular haemorrhage or white matter damage) on cranial ultrasound scan or other imaging
- Seizures outside of 48 hours the procedure
- Pulmonary hypertension
- Hydrocephalus
- Respiratory distress syndrome
- Bronchopulmonary dysplasia or chronic lung disease
- Retinopathy of prematurity
- Early or late-onset Sepsis
- Patent ductus arteriosus (PDA)
- Pulmonary haemorrhage
- Pneumothorax
- Anaemia
- Hyperbilirubinaemia/jaundice
- Hypoglycaemia
- Hyperglycaemia
- Coagulopathy
- Liver cholestasis
- Liver failure
- Hypotension
- Hypertension
- Impaired renal function
- Extravasation injury
- Fractures
- Return to hospital for suspected or actual shunt malfunction or other neonatal condition unrelated to hydrocephalus after discharge from the neonatal unit, (unless readmission following initial discharge from hospital for grade 3 and above events)

6.1.2.2 'Unforeseeable SAEs' – (All SAEs not listed as 'Foreseeable SAEs')

All other SAEs occurring in trial participants which are not listed as Foreseeable SAEs in Section 6.1.2.1 are classed as unforeseeable SAEs and must be reported immediately after site staff become aware of the event (in no circumstances should this notification take longer than 24 hours) (see section 6.3).

6.2 Notifiable Adverse Events

The following adverse events should be reported within 5 working days using the Notifiable AE CRF:

- 1. New bleed identified on post-operative cranial ultrasound (CTCAE grade 2 and above)
- 2. Unexpected return to theatre for temporising device dysfunction, infection or CSF leak (CTCAE grade 3 and above). CSF infections will be monitored closely and reviewed at Trial Management Group meetings.
- 3. Return to theatre for insertion of an additional temporising device to treat loculated hydrocephalus (CTCAE grade 3 or above) or for a second endoscopic procedure to deloculate the ventricles
- 4. Confirmed or presumed infection associated with the trial procedure (grade 3 and above). This will include superficial (wound) and deep (CNS) infection. Confirmed infection will be where a micro-organism thought to be causative is isolated and presumed is when a micro-organism is not isolated, but the treating clinical team commences antibiotics. Of note, preterm infants may have many sources of infection and the **reporting here is confined to infection associated with the procedure (grade 3 and above).**
- 5. New development of seizures within 48 hours of the intervention (NEL) (grade 3 and above)
- 6. New development of focal neurological deficits within 48 hours of the intervention (NEL) (grade 3 and above)
- 7. Abandoned NEL procedure

Only non-serious AEs which constitute a notifiable event (listed above) should be reported to CCTU (via the trial database) within 5 working days.

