5.1.2 Secondary Outcomes

The secondary outcome measures are:

- 1. Developmental Measures:
 - a. Motor quotient (MQ): Age equivalent motor score of the Bayley IV divided by corrected age at assessment, measured at 2 years' corrected age
 - b. Language quotient (LQ): Age equivalent language score of the Bayley IV divided by corrected age at assessment, measured at 2 years' corrected age
- 2. Other neurological and functional assessments conducted during the 2-year follow-up visit:
 - a. Presence of seizures during the first 2 years and use of anticonvulsant medication at 2 years.
 - Presence of cerebral palsy (+ accompanying Gross Motor Function Classification System (GMFCS) grade and deficit distribution map using the Classification of SCPE
 - c. Assessment of hearing and vision (British Association of Perinatal Medicine classification)
 - d. Parent report:
 - i. Brief Infant Toddler Social Emotional Assessment (BITSEA)
 - ii. Quantitative Checklist for Autism in Toddlers (Q-CHAT)
- 3. Mortality up to 2 years corrected age.
- 4. NEL & VP shunt related outcomes:

- a. Safety of NEL: Number of Adverse Events, where Adverse Events would include (and not limited to) secondary bleeding in the brain, post-operative infections, temporising device survival, mortality, stroke, seizures, electrolyte disturbances, CSF leak, unexpected readmissions or return to theatre.
- b. Number and type of further surgical procedures, including revision of the temporising drainage device (VAD or VSG), addition of a second temporising device, surgery for loculated or isolated ventricles, and revisions of the VP shunt, if implanted, until two years' corrected age. These infants often need multiple shunt revisions during their first two years of life. We will have a separate CRF to record data related to these unexpected presentations and procedures.
- c. Requirement for permanent VP shunt insertion at 6 months' corrected age. (This is at the discretion of the treating team in the participating centre, according to routine clinical care).
- 5. Quality of life and health economic assessments:
 - a. Health-Related Quality of Life (HRQoL) in children: TNO-AZL Preschool Children's Quality of Life (TAPQOL) to be assessed at 12-months and 2 years' corrected age
 - b. HRQoL in primary caregiver: EuroQoL EQ-5D-5L to be assessed at baseline, 6 months, 12 months- and 2 years' corrected age

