6.4 Investigator responsibilities

All non-serious AEs, whether expected or not, should be recorded in the patient's medical notes. Only non-serious AEs which constitute a notifiable event (listed in section 6.2) should be reported to CCTU (via the trial database) within 5 working days.

All Foreseeable SAEs that are **casually related** to the trial intervention (NEL) or trial procedures should be reported to CCTU immediately and no later than 24 hours after the site staff becomes aware of the event.

All Unforeseeable SAEs (regardless of causal relationship to trial intervention NEL or trial procedures) should be reported to CCTU immediately and no later than 24 hours after the site staff becomes aware of the event.

Please refer to Appendix II for Safety Reporting Flowchart.

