6.4.1.2 Severity or Grading of Adverse Events

The severity of all AEs (serious and non-serious) in this trial should be graded using the gradings in the Common Terminology Criteria for Adverse Events (CTCAE) Version 5.0 (2017):

Grades for AEs according to the CTCAE are:

Grade 1: Mild; asymptomatic or mild symptoms; clinical diagnostic observations only; intervention not indicated.

Grade 2: Moderate; minimal, local or non-invasive intervention indicated.

Grade 3: Severe or medically significant but not life threatening; hospitalisation or prolongation of hospitalisation indicated; disabling.

Grade 4: Life threatening consequences; urgent intervention indicated.

Grade 5: Death related to AE.

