6.4.1.4 Expectedness

If there is at least a possible involvement of the trial intervention (NEL), the sponsor will assess the expectedness of the event. If information of expectedness is provided by the investigator this should be taken into consideration by the sponsor. An unexpected adverse event is one not reported in Table 6 NEL Risks and mitigations (**Section 6.3.1.5**).

6..1.5 Risks associated with NEL

The risks associated with NEL for the ENLIVEN-UK trial are listed in Table 6 (NEL risks and mitigations) below:

Table 6. NEL risks and mitigations.

POTENTIAL RISK	RISK MANAGEMENT
Infection	Procedure in strict sterile conditions in operating theatre as per standard practice. Peri-operative antibiotics are given and the choice of agent and duration will vary according to local guidelines.
Secondary bleeding	There is a clear consensus on surgical protocol to ensure maximal safe washout without causing secondary bleeding in the ventricles or in the brain. The surgeon should stop when they feel they have achieved a 'maximal safe washout' as defined in the consensus guideline (28).
Stroke	Procedure-related brain injury risk has not been reported with NEL and therefore, the

	risk is low. It will be identified if it occurs on
	the post-operative ultrasound scan.
CSF leak	Standard closure techniques will be used to
	protect against CSF leak and, if it develops,
	will be managed at the discretion of the
	treating surgeon.
Seizures	Seizures (up to CTCAE Grade 3) can arise
	as a result of the initial IVH or procedure-
	related brain injury. These have been
	reported with NEL but the risk is low. If it
	occurs, it will be managed at the discretion of
	the treating medical team including
	neurosurgeon and neonatologist.
Temporising device dysfunction	The TD may stop working adequately due to
	either blockage, insufficient drainage or
	infection. At this stage, the clinical team will
	make an assessment as to whether it needs
	to be revised or whether a permanent
	ventriculoperitoneal shunt needs to be
	placed. This management will remain at the
Flootrolyte/Codings imbalance	discretion of the treating neurosurgical team.
Electrolyte/Sodium imbalance	The use of irrigating solution may lead to
	disturbances in the serum level of sodium
	and other electrolytes. This will be mitigated
	by using appropriate irrigating solutions, such
	as Ringer Lactate or artificial CSF and by
	monitoring electrolyte levels in the serum as

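### Asymptomatic, non-serious new bleeds on the mandated post-operative scan fall below the notifiable threshold, so they do not enter the adverse event count behind safety outcome 4a

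*Protocol*

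**What the plan says.** Four provisions of the protocol act together.

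- Section 6.2, item 1, sets the notifiable event: "New bleed identified on post-operative cranial ultrasound (CTCAE grade 2 and above".
- Section 6.4.1.2 gives the grades: "Grade 1: Mild; asymptomatic or mild symptoms; clinical diagnostic observations only; intervention not indicated" and "Grade 2: Moderate; minimal, local or non-invasive intervention indicated".
- Section 6.1.1 limits what is collected: "Only adverse events deemed as serious (see section 6.1.2) or as notifiable event (see section 6.2) will be recorded for the trial". For the rest, section 6.4 says: "All non-serious AEs, whether expected or not, should be recorded in the patient's medical notes".
- Section 5.1.2, outcome 4a, defines the safety of NEL as a number of adverse events: "Adverse Events would include (and not limited to) secondary bleeding in the brain". Secondary bleeding is the first component named.

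The scan itself is not optional. Section 3.6 and Table 1 schedule a cranial ultrasound at 24-48 hours after surgery in both arms, and section 5.3.1 requires ultrasound images to be submitted for all infants.

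**The concern.** The post-operative ultrasound is where a new bleed would be found, and Table 6 relies on the same scan to identify stroke. The notifiable rule then filters what the scan shows by a grade that rests on symptoms and on whether intervention is indicated. A finding made only on imaging can fall below that filter however clear it is on the scan.

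Safety is part of the trial's objective (section 1.2). Section 1.4 lists further haemorrhage within the ventricles among the risks of NEL, and section 1.1.1 gives a reduced risk of secondary haemorrhage as a reason to prefer NEL to the earlier irrigation technique. A low bleed count in the final report would be read as evidence on that point. It should be clear whether such a count means that few bleeds occurred or that only those above a grade were collected. A statistical analysis plan cannot settle this afterwards for events that never reached the database.

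**Working it through.** **Step 1: follow one event through the rules.** Take a new bleed on the 24-48 hour scan with no symptoms and no intervention indicated.

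| Question | Provision | Result |
|---|---|---|
| What grade is it? | 6.4.1.2 | Grade 1; grade 2 needs at least minimal intervention |
| Is it notifiable? | 6.2, item 1 | No; the floor is grade 2 |
| Is it an SAE? | 6.1 (Table 4), 6.1.2.1 | Only if a seriousness criterion is met; the imaging entry in 6.1.2.1 lists foreseeable SAEs, so seriousness comes first |
| If not serious, is it recorded for the trial? | 6.1.1, 6.4 | No; medical notes only |
| Does it count in outcome 4a? | 5.1.2 | The outcome is a number of adverse events, and this one has no event record |

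**Step 2: check the other routes.**

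- *Stored images.* Section 7.6.2 sends ultrasounds to UCL for secondary outcome analysis. No outcome in section 5.1.2 is defined from imaging, and no reading for new bleeds is specified.
- *TMG review.* Sections 4.7.1 and 6.5 have the TMG review post-operative scans at least quarterly, to look at variability in the surgery. Section 5.3.1 describes this review for the post-NEL scans, with feedback on technique. Nothing says that its findings enter the event count or the IDMC reports.

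**Step 3: illustrate the size.** The protocol states no figure that could be reproduced here. Inputs:

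- n = 50 per arm (section 3.3).
- p = 5%, the upper limit that section 1.4 gives for the risks in either arm.
- f = the share of new bleeds that are grade 1 and not serious. The protocol does not give f; 25%, 50% and 75% are assumptions.

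Expected recorded bleeds per arm = n × p × (1 − f). Chance of recording none in an arm = (1 − p(1 − f))^n.

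| f | Expected recorded | Chance of none |
|---|---|---|
| 0 (all grades recorded) | 50 × 0.05 = 2.5 | 0.95^50 = 7.7% |
| 25% | 50 × 0.0375 = 1.88 | 0.9625^50 = 14.8% |
| 50% | 50 × 0.025 = 1.25 | 0.975^50 = 28.2% |
| 75% | 50 × 0.0125 = 0.62 | 0.9875^50 = 53.3% |

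At an assumed p of 10%, the expected 5.0 becomes 3.75, 2.5 or 1.25.

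**Step 4: illustrate sensitivity to a true difference.** Assume true rates of 5% and 15% and the same f in both arms. At f = 50% the recorded rates are 2.5% and 7.5%, so the recorded difference falls from 10 to 5 percentage points. Power for a two-sided 5% comparison of two proportions with 50 per arm (normal approximation) falls from 38% to 21%. It is low in either case, so what is lost is mainly descriptive information.

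**The case against.** The strongest reply is that the threshold is deliberate and that the protocol has other safeguards. Section 6.1.1 explains restricted recording by the high background of adverse events in these infants. Bleeding has the lowest explicit floor in section 6.2; the other graded items start at grade 3. Images from both arms are held centrally, so silent bleeds could be recovered. The rate is expected to be low, and even full capture gives about 2.5 bleeds per arm at the protocol's upper figure. All of this stands. It limits the size of the problem, but none of it puts a silent bleed into the count.

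Four stronger readings are tempting, and the protocol does not support them.

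- *That scan-detected bleeds in general go unrecorded.* Grade 2 and above go on the notifiable event CRF. Serious bleeds go through the SAE route in either arm. Seriousness includes other important medical conditions, a matter of medical judgement, so some investigators may report a silent bleed that way.
- *That the comparison between arms is biased.* The floor is nominally the same in both arms. Site staff know the allocation (section 8.2.3) and apply the boundary between grades 1 and 2, so different application by arm is possible, but nothing in the protocol shows it.
- *That the TMG would be unaware of more bleeding, or that a new infarct has no reporting route.* The TMG sees post-operative scans at least quarterly. White matter damage on imaging is a listed foreseeable SAE if serious, other serious strokes are unforeseeable SAEs, and item 6 of section 6.2 covers grade 3 or higher focal deficits within 48 hours of NEL. The remaining gap for a new lesion on the scan is the same silent, non-serious one.
- *That the count would read 0 or 1 whatever the true rate.* With a true rate of 20% and half the bleeds silent, the recorded rate is 10%, 5 bleeds are expected per arm, and the chance of 0 or 1 is 0.9^50 + 50 × 0.1 × 0.9^49, about 3%.

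**Conclusion.** The point holds in a narrow form. Read together, sections 6.1.1, 6.2 (item 1), 6.4 and 6.4.1.2 leave asymptomatic, non-serious new bleeds on a mandated scan outside trial event recording, while outcome 4a counts events and names secondary bleeding first. This follows from the protocol's wording and needs no assumption.

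The size of the under-count does need one. It depends wholly on the share of silent bleeds, for which the protocol gives no value, and the figures above show only what a range of shares would do. The consequence is a lower absolute count and less sensitivity: a reassuring zero in an arm becomes easier to obtain, at 28.2% rather than 7.7% if the rate is 5% and half are silent. It does not invalidate the safety comparison. The change is worth making because it is cheap, not because the loss is shown to be large.

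**What to change.** Change data capture only; clinical care is untouched.

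- Reword section 6.2, item 1, to cover any new or extended intracranial haemorrhage, or new parenchymal lesion, on the post-operative scan compared with the pre-operative scan, in both arms and irrespective of grade. Enter it on the existing notifiable event CRF with its CTCAE grade.
- Report any-grade and grade 2+ bleeding separately by arm, in outcome 4a and to the IDMC.
- Reconcile item 1 with the intracranial abnormality entry in section 6.1.2.1, so that sites know which form a new bleed on the scan belongs on.

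The scan is already scheduled and its images submitted for every infant, so the cost is one reworded item, a few CRF fields and a few more notifiable event forms.

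### Non-serious CSF leaks managed without theatre, and non-serious procedure-related infections below grade 3, have no stated route into the adverse event data, although safety outcome 4a names both

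*Protocol*

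**What the plan says.** **The outcome.** Protocol 5.1.2, item 4a, defines the safety of NEL as the number of adverse events. Its components include "secondary bleeding in the brain, post-operative infections, temporising device survival, mortality, stroke, seizures, electrolyte disturbances, CSF leak, unexpected readmissions or return to theatre". CSF leak, post-operative infection and return to theatre are thus listed side by side.

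**The recording rule.** Section 6.1.1 states: "Only adverse events deemed as serious (see section 6.1.2) or as notifiable event (see section 6.2) will be recorded for the trial". Section 6.4 (Investigator responsibilities) agrees: other non-serious events go into the medical notes and are not reported to the trials unit.

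**The notifiable list (6.2).** Item 2 is "Unexpected return to theatre for temporising device dysfunction, infection or CSF leak (CTCAE grade 3 and above"). CSF leak has no item of its own, and Section 3.6 repeats the same trigger for unscheduled visits. Item 4 is "Confirmed or presumed infection associated with the trial procedure (grade 3 and above"), and adds: "This will include superficial (wound) and deep (CNS) infection".

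**The grading scale (6.4.1.2).** The level just below the floor used in items 2 and 4 reads "Grade 2: Moderate; minimal, local or non-invasive intervention indicated", whereas the floor itself reads "Grade 3: Severe or medically significant but not life threatening; hospitalisation or prolongation of hospitalisation indicated; disabling".

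**The serious route (6.1.2.2).** "All other SAEs occurring in trial participants which are not listed as Foreseeable SAEs in Section 6.1.2.1 are classed as unforeseeable SAEs". Neither CSF leak nor wound infection is on the foreseeable list.

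**The concern.** An outcome can count only what reaches the database. Two components named in 4a pass through filters that 4a does not mention.

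For CSF leak the filter is a management decision. Table 6 leaves the handling of a leak to the treating surgeon, and 8.2.3 says that surgeon cannot be blinded. The notifiable count therefore reflects whether an unblinded clinician chose to re-operate, not whether the infant leaked. This also sits badly with 6.1.1, which says a procedure is not an adverse event and that the condition leading to it is.

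For infection the filter is a severity grade assigned by unblinded site staff.

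Safety is half of the primary objective (1.2), infection and CSF leak are both named risks of NEL (1.4 and Table 6), and the IDMC relies on these data (6.5, 8.3.3). No later analysis plan can restore events that were never sent to the database.

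**Working it through.** No stated figure needs reproducing. The check follows each kind of event through the rules, then illustrates the size.

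**Step 1. Routes for a CSF leak**

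| Leak | Notifiable (6.2) | SAE (6.1.2.2) | In the AE data? |
|---|---|---|---|
| Serious, with or without theatre | if item 2 is met | yes, unforeseeable, within 24 hours | yes |
| Not serious, unexpected return to theatre, grade 3 or above | yes, item 2 | no | yes |
| Not serious, managed without theatre | no | no | no stated route |

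**Step 2. Routes for a procedure-related infection, superficial or deep**

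| Infection | Notifiable (6.2) | SAE (6.1.2.2) | In the AE data? |
|---|---|---|---|
| Serious | if grade 3 or above | yes | yes |
| Not serious, grade 3 or above | yes, item 4 | no | yes |
| Not serious, grade 1 or 2 | no | no | no stated route |

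**Step 3. How far the serious route closes the gap.** The footnotes to Table 4 count hospitalisation as serious only when it is additional to, or longer than, what standard care would involve. These infants are already inpatients. A leak or infection treated within the expected stay does not meet that criterion. If no other criterion applies, reporting rests on the important-medical-condition judgement, made by staff who know the arm. The grade 3 wording in 6.4.1.2 is itself close to the hospitalisation criterion, so a grade 3 floor on the notifiable list adds little for non-serious events.

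**Step 4. Other places the event might appear.** Wound-site checks are scheduled at 24 to 48 hours, at term-equivalent age, at 2 years and at unscheduled visits (Table 1). Section 5.1.2, item 4b, plans a separate CRF for unexpected presentations and procedures. The protocol does not say that either feeds the 4a count.

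**Step 5. Illustration of size**

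Inputs: n = 50 per arm (3.3); p = 5%, the upper bound in 1.4, read here as a rate per complication (an assumption, since the text does not clearly say so); f = the fraction captured (an assumption, as the documents give none).

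- Expected true events per arm: 50 × 0.05 = 2.5.
- Expected recorded events: 50 × p × f.
- Chance of recording at least one event in an arm: 1 − (1 − p × f)^50.

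| Captured f | Recorded per arm | Lost per arm | Chance of at least one recorded |
|---|---|---|---|
| 100% | 2.5 | 0 | 0.92 |
| 75% | 1.9 | 0.6 | 0.85 |
| 50% | 1.25 | 1.25 | 0.72 |
| 25% | 0.6 | 1.9 | 0.47 |

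With so few events, losing one or two per arm can decide whether a complication is seen at all.

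**The case against.** **The restriction is reasoned.** Section 6.1.1 explains that preterm infants in intensive care have many foreseeable adverse events, so collection is limited to serious and notifiable ones. Items 5 and 6 of 6.2 use the same grade 3 floor. This stands as a reason for some threshold. It does not explain why 4a names components that the threshold then removes without saying so, or why the leak trigger is a procedure.

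**A reader might infer that a leak is recorded only if the infant returns to theatre.** The documents do not support that. A leak meeting any seriousness criterion is an unforeseeable SAE, reportable within 24 hours whether or not theatre follows. The gap is confined to non-serious leaks.

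**A reader might also infer that item 4 contradicts itself, including superficial wound infection in one sentence and excluding it by grade in another.** That does not hold either. Superficial and deep describe depth; grade describes severity. A superficial infection that is medically significant or prolongs the stay is grade 3 and is covered. The limit appears twice in item 4, so it is deliberate. The item is narrow, not inconsistent.

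**The infection threshold is partly a matter of preference.** This is fair. Stating the restriction openly in 4a would be enough.

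**Conclusion.** The point holds in a limited form. Non-serious CSF leaks managed without theatre, and non-serious procedure-related infections of grade 1 or 2, have no stated route into the adverse event data although 4a names both categories. The leak part is the stronger: its notifiable trigger is a discretionary act by an unblinded surgeon and departs from the protocol's own rule that the condition is the event.

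The illustrated loss of 0.6 to 1.9 of 2.5 expected events per arm rests on two assumptions: that under 5% applies to each complication, and that 25% to 75% of events go unrecorded. A reader might go further and infer that the arms will be compared unfairly. Unblinded discretion makes that possible, but nothing in the documents indicates that surgeons would re-operate or grade differently by arm, so no size can be given for such a bias.

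This affects components of one secondary outcome with few expected events. It is worth correcting because the correction is cheap.

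**What to change.** Reconcile 5.1.2 (4a), 6.1.1 and 6.2, and the matching sentence on unscheduled visits in 3.6. The changes concern recording only, not care.

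1. **CSF leak.** Make post-operative CSF leak its own notifiable item in both arms, irrespective of how it is managed. Record return to theatre as a separate data field, since 4a lists it as its own component. Name the scheduled wound-site checks as a source. A grade floor for leaks would bring part of the management judgement back, because the scale in 6.4.1.2 is worded largely by the intervention indicated.
2. **Infection.** Choose one: record procedure-related infections from grade 2, as item 1 of 6.2 already does for new bleeds; or state in 4a that only serious or grade 3 and above infections are counted.

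**Cost.** Wording in the sections above, one CRF field and a few more notifiable reports. Reading the under-5% figure per complication, at most about 100 × 0.05 = 5 infants in the whole trial would have each complication, and some of these would be reported already.
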